10. SAFETY ANALYSES

All safety analyses will be based on the Safety population. Adverse events will be monitored by the investigator and the subject. The safety analyses of laboratory parameters will include descriptive statistics and AEs will include frequency counts and percentages. Summaries of AEs will be generated by type (AE or SAE), body system and preferred term, severity, and relationship to study product.

10.1 Study Drug Administration

Treatment compliance will be assessed via direct observation by the study investigator who is responsible for study drug administration. The cell dose and exact time of injection will be recorded. Study drug administration responses will be tabulated for each treatment according to questions asked in the CRF, including whether the total dose was administered, whether there were any dose interruptions were there any AEs observed, were the subject's vital signs comparable to pre-treatment of study drug injection, was the subject's IOP measurement less than 30 mm post treatment of study drug injection and was the subject prescribed topical treatment after treatment of study drug injection.

10.2 Adverse Events

All adverse event summaries will be restricted to Treatment Emergent Adverse Events (TEAE), which are defined as those AEs that occurred after dosing and those existing AEs that worsened during the study. If it cannot be determined whether the AE is treatment emergent due to a partial onset date then it will be counted as such. Verbatim terms on case report forms will be mapped to preferred terms and system organ classes using the Medical Dictionary for Regulatory Activities (MedDRA) (version 18.1).

Each adverse event summary will be displayed by treatment group. Summaries that are displayed by system organ class and preferred terms will be ordered by descending order of incidence of system organ class and preferred term within each system organ class. Summaries of the following types will be presented:

- Subject and event incidence of TEAEs by MedDRA system organ class and preferred term.
- Subject incidence of TEAEs by MedDRA system organ class, preferred term, and highest severity. At each level of subject summarization a subject is classified according to the highest severity if the subject reported one or more events. Categories of severity will be "Mild", "Moderate", "Severe" and "Life Threatening" in this summary. The "Life Threatening" column will only be shown if at least 1 life-threatening AE is reported. If any AEs are reported with missing severity, then a footnote will be added to indicate how many AEs with missing severity were reported.
- Subject and event incidence of related TEAEs by MedDRA system organ class and preferred term. Related AEs are those reported as "Related", "Possibly Related" or relationship was not reported. At each level of subject summarization a subject is classified according to the closest relationship if the subject reported

one or more events. AEs with a missing relationship will be considered related for this summary.

• Subject and event incidence of serious TEAEs by MedDRA system organ class and preferred term.

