9.0 SAFETY CONSIDERATIONS

9.1 Adverse Events

An AE is defined for this study as any untoward medical occurrence in a subject who is administered clinical study material. The occurrence of this event does not necessarily have a causal relationship with study product. An AE can therefore be any unfavorable and unintended sign (including an abnormal laboratory finding), symptom, or disease temporally associated with the use of a study (investigational) product, whether or not related to the study product.

Examples of an AE include:

- Exacerbation of a chronic or intermittent pre-existing condition, including either an increase in frequency or intensity of the condition
- Significant or unexpected worsening or exacerbation of the condition/indication under study (RP)
- A new condition detected or diagnosed after study product administration even though it may have been present prior to the start of the study
- Signs, symptoms, or clinical sequelae of a suspected overdose of either study product or a concurrent medication
- Pre- or post-treatment events that occur as a result of protocol-mandated procedures
- Antibody development

An AE does not include:

- Medical or surgical procedures (e.g., colonoscopy or biopsy); the medical condition that leads to the procedure is an AE
- Social or convenience hospital admissions where an untoward medical occurrence did not occur
- Day-to-day fluctuations of a pre-existing disease or conditions present or detected at the start of the study that do not worsen
- The disease/disorder being studied (RP), or expected progression, signs, or symptoms of the disease/disorder being studied unless more severe than expected for the subject's condition

All AEs that occur after informed consent is signed will be recorded in the source documents and on the appropriate CRF page. The information to be collected includes the nature, date and time of onset, intensity (mild, moderate, severe, life-threatening, death), duration, causality (relationship to investigational product), and outcome of the event. Even if the AE/SAE is assessed by the Investigator as not reasonably attributable to study product, its occurrence must be recorded in the source documents and on the appropriate page of the CRF.

Treatment-emergent AEs will be defined as AEs that occur after the treatment with jCell.

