Serious AE	An AE occurring at any dose that: results in death; is a life-threatening experience; requires inpatient hospitalization or prolongation of an existing hospitalization; results in a persistent or significant disability/incapacity; or is a congenital anomaly/birth defect in the offspring of a subject who received study
Treatment-emergent AE	AEs with an onset time after the initial dose of study
	drug.

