The most conservative approach will be systematically considered. If the AE onset date is missing / incomplete, it is assumed to have occurred during the study treatment phase (i.e., considered a TEAE) except if the partial onset date or other data such as the stop date, indicates differently. Similarly, a medication with partial start and stop dates could be considered as both a prior and concomitant treatment.

The following algorithms will be applied to missing and incomplete start and stop dates:

Start Dates

- If the day portion of the start date is missing, then the start date will be estimated to be equal to the date of first dose of study drug, provided the start month and year are the same as the first dose of study drug and the stop date is either after the first dose of study drug or completely missing. Otherwise, the missing day portion will be estimated as '01'.
- If both the day and month portions of the start date are missing, then the start date will be estimated to be equal to the date of first dose of study drug, provided the start year is the same as the first dose of study drug and the stop date is either after the first dose of study drug or completely missing. Otherwise, the event will be assumed to start on the first day of the given year (e.g., ??-??-2013 is estimated as 01-JAN-2013).
- If the start date is completely missing and the stop date is either after the dose of study drug or completely missing, the start date will be estimated to be the day of study drug dosing. Otherwise, the start date will be estimated to be the first day of the same year as the stop date. All other non-AE and non-concomitant medication day calculations where only partial dates are available will be handled as follows: the first day of the month will be used in the calculations if the day part of a start date is missing while January 1 will be employed if both the month and day parts of a start date are missing.

Stop Dates

• If only the day of resolution is unknown, the day will be assumed to the last of the month (e.g., ??-JAN-2013 will be treated as 31-JAN-2013).

jCyte, Inc	Statistical Analysis Plan
Protocol No. JC-01	08Nov2017

- If both the day and month of resolution are unknown, the event will be assumed to have ceased on the last day of the year (e.g., ??-???-2013 will be treated as 31-DEC-2013).

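### The SAP holds two conflicting definitions of a treatment-emergent AE, and its start-date rule can drop a dose-day event from the AE tables

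*SAP*

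**What the plan says.** **Definitions.** Protocol 9.1 states: "Treatment-emergent AEs will be defined as AEs that occur after the treatment with jCell". The glossary entry in the SAP Definitions says the same in other words: "AEs with an onset time after the initial dose of study" drug. SAP 10.2 limits all AE summaries to treatment-emergent events and adds a second limb: these are events "which are defined as those AEs that occurred after dosing and those existing AEs that worsened during the study".

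**When recording starts.** Protocol 9.1: "All AEs that occur after informed consent is signed will be recorded in the source documents". Section 8.1.1 starts monitoring when a study number is assigned, which Section 5.0 places at consent. Table 2, however, shows AE collection only from Day 0, and Sections 7.1 to 7.3 do not list it. It first appears in 7.4, after the injection.

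**Incomplete onset dates.** SAP 10.2: "If it cannot be determined whether the AE is treatment emergent due to a partial onset date then it will be counted as such". Appendix A opens with a conservative principle in line with this, under which such an event is "considered a TEAE) except if the partial onset date or other data such as the stop date, indicates differently". The first two start-date rules then say "the start date will be estimated to be equal to the date of first dose of study drug", on condition that the known part of the onset date matches the dose and that "the stop date is either after the first dose of study drug or completely missing". The third rule, for a wholly missing onset, uses essentially the same stop-date condition. If the condition fails, onset becomes day 01 of the month, or 1 January.

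**The concern.** Safety and tolerability is the primary objective, and treatment-emergent status decides whether an event enters Tables 14.3.1.1 to 14.3.1.4. If one SAP gives two answers for the same event, the programmer has to choose between them, possibly with open-label events already in view. The layouts of these four tables carry no footnote saying which rule applies.

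Misclassification can run both ways. Worsening after the injection of an event that began before it can be left out. Worsening confined to the period before injection can be let in, because the second limb of 10.2 refers to the study as a whole and not to the injection. Pre-injection AEs are foreseeable: protocol 9.1 counts events caused by protocol-mandated procedures before treatment, and the baseline visit includes fluorescein angiography.

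The date rules raise a separate, narrower problem. They are meant to keep doubtful events in, but one branch sends an event that ended on the day of injection to a date normally before it.

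**Working it through.** The plan states no figure on this point, so there is none to reproduce. The check applies each rule as written to test events, then sizes one change of classification.

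**1. Events with complete dates**

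| Event | Protocol 9.1 | SAP Definitions | SAP 10.2 |
|---|---|---|---|
| Onset after dose | in | in | in |
| Onset before dose, no worsening | out | out | out |
| One record, onset before dose, worsens after dose | out | out | in |
| One record, onset after consent, worsens only before dose | out | out | in, as worded |

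Protocol 9.1 and the SAP Definitions agree in every row. SAP 10.2 departs from both in the last two.

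**2. Events with incomplete onset dates** (dose date assumed to be 15 March 2016, for illustration)

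| Known onset | Stop date | Appendix A onset | Relation to dose date |
|---|---|---|---|
| March 2016 | ongoing or missing | 15 March 2016 | equal |
| March 2016 | 20 March 2016 | 15 March 2016 | equal |
| 2016 only | ongoing or missing | 15 March 2016 | equal |
| March 2016 | 15 March 2016 | 1 March 2016 | before |
| nothing | 15 March 2016 | 1 January 2016 | before |
| March 2016 | 10 March 2016 | 1 March 2016 | before (correct: it ended before the dose) |

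In the fourth and fifth rows the true order of onset and injection is unknown. SAP 10.2 would count the event; the imputed date puts it before the dose. The listing layout shows an end date without a time, so a stop on the dose day cannot be shown to fall after the injection. The imputed day would not precede the dose only if the injection itself fell on the first of the month (or, for the fifth row, on 1 January).

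In the first three rows the imputed onset equals the dose date. Appendix A intends these as treatment-emergent, but a strict comparison for onset after the initial dose, as the Definitions read, would reject them.

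**3. Size of one reclassification**

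Inputs: up to 28 subjects, 14 per cohort, planned as 4 + 4 + 3 + 3 by dose level (protocol synopsis and Sections 3.1.1 and 3.1.2). The change in a row percentage is 100/n when the subject has no other qualifying event in that row:

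- n = 4: 100/4 = 25.0 points
- n = 3: 100/3 = 33.3 points
- n = 28: 100/28 = 3.6 points

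If the subject already counts in that row through another event, the subject percentage does not move.

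**The case against.** The strongest reply is that the exposure is narrow and nothing is hidden. Protocol 9.1 makes exacerbation of a pre-existing condition an AE in itself, so worsening entered as a new record after injection counts under every definition. SAP 10.2 restricts summaries, not listings: Listing 16.2.7.1 still shows each AE with its onset study day, severity and relationship. The drug-administration table separately reports whether AEs were observed, with no treatment-emergent filter. The rule for suspending the study on Grade 3 or 4 events does not depend on treatment-emergent status. For the date rule, the reply is that the conservative principle governs, and that an unknown onset day combined with a known stop on the injection day is remote, since Section 7.4 collects AEs and the exact injection time that day.

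Most of this stands as a limit on size. It does not remove the conflict. No text requires worsening of an AE already on record to be entered as a new one, and a listing does not correct a summary table. The principle in Appendix A does not say that it overrides the algorithms beneath it, so the appendix disagrees with itself.

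A reader might infer more than the documents support:

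- **Four different definitions.** There are two, plus a date rule that shares the intent of 10.2 and departs from it in a corner case and a tie.
- **Worsening cannot be identified in the data.** The listing layout has one onset, one end date and one severity per AE, but Appendix A allows variables to be added and the CRF is not in the documents.
- **A known share of subjects is affected.** The documents give no basis for any frequency.
- **Inclusion attributes the event to jCell.** Relatedness is handled separately, in Table 14.3.1.3.

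**Conclusion.** The concern holds in this limited form. The SAP contradicts its own Definitions, and protocol 9.1, on whether worsening of an existing AE counts, and the wording of 10.2 also admits worsening that ended before the injection. The exposed events are AEs kept as one record with onset before injection. Separately, the start-date rules contradict 10.2 and their own principle for an incomplete onset with a stop on the dose day, and leave a tie when onset is imputed to the dose date.

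The effect is up to 25.0 or 33.3 points in a planned dose column and 3.6 points in a total of 28, per reclassified subject. This assumes the planned group sizes are reached (28 is a maximum and the two higher dose levels are optional) and that the subject has no other qualifying event in the row. How often it would happen is unknown, and the affected events remain visible in the AE listing. It should be corrected because it touches the primary safety tables and the repair is small.

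**What to change.** - Put one definition in both the SAP Definitions and 10.2: an AE with onset at or after the injection, or an AE present before injection whose severity or seriousness increases after it. State that worsening only before injection does not qualify.
- Identify post-injection worsening as a new AE record dated at the worsening.
- In the three Appendix A start-date rules, change the stop-date condition from 'after' to 'on or after the date of' first dose. State that onset on the dose day with unknown time counts as treatment-emergent.
- Reconcile Table 2 and Sections 7.1 to 7.3 with 8.1.1 and 9.1 on when AE recording starts, since the pre-injection state is needed to judge worsening.

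The cost is a few lines of wording, one programming rule, and a check of AE records that began before injection. The downside is that a few more events may appear as treatment-emergent.

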3.2.2 Safety Endpoints

The primary goal of the study is to evaluate the safety and tolerability of jCell injection: The criteria that will be used to establish safety include:

- Slit-lamp findings, i.e., anterior chamber cell or flare; acute cataract development or progression in phakic patients, vitreous haze.
- Absence of tumor formation, overt immune rejection, decrease in BCVA attributable to treatment
- Absence of clinically significant, persistent increase in intraocular pressure (>10 mm Hg above baseline or IOP > 25 mm Hg), clinically significant epiretinal membrane, retinal detachment, neovascularization, or endophthalmitis
- No clinically significant adverse events attributable to investigational product (jCell) injection
- Patient comfort (no intolerable pain related to procedure)

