No	n (%)	n (%)	n (%)	n (%)	n (%)
Any Dose interruptions?					
Yes	n (%)	n (%)	n (%)	n (%)	n (%)
No	n (%)	n (%)	n (%)	n (%)	n (%)
Were any Adverse Events observed?					
Yes	n (%)	n (%)	n (%)	n (%)	n (%)
No	n (%)	n (%)	n (%)	n (%)	n (%)
Subject Vital Signs comparable to pre injection levels?					
Yes	n (%)	n (%)	n (%)	n (%)	n (%)
No	n (%)	n (%)	n (%)	n (%)	n (%)
Subject IOP < 30mm post treatment of injection?					
Yes	n (%)	n (%)	n (%)	n (%)	n (%)
No	n (%)	n (%)	n (%)	n (%)	n (%)
Subject Prescribed Topical Treatment after Study Drug					
Yes	n (%)	n (%)	n (%)	n (%)	n (%)
No	n (%)	n (%)	n (%)	n (%)	n (%)
cludes both Cohorts 1 and 2.					
gram.sas date time					

	Safety PopulationSafety PopulationCohort 1Cohort 2Class / rm $(N=)$ $(0.5 x 10^6 hRPC$ $(N=)$ $(N=)$ Total [1] $(N=)$ SubjectsEventsSubjectsEventsSubjectsEventsSubjectsEventsSubjectsEventsSubjectsEventsSubjectsEventsSubjectsEventsSubjectsEventsrting at Least One TEAEn (%)xxn (%)<									
		Coh	ort 1			Coh	ort2			
System Organ Class /	0.5 x 10	⁶ hRPC			0.5 x 10 ⁶	hRPC			Tota	ıl ^[1]
Preferred Term	(N=	=)	(N	=)	(N=	=)	(N	J=)	(N	=)
	Subjects	Events	Subjects	Events	Subjects	Events	Subjects	Events	Subjects	Events
Subjects Reporting at Least One TEAE	n (%)	XX	n (%)	XX	n (%)	XX	n (%)	XX	n (%)	xx
System Organ Class 1	n (%)	XX	n (%)	XX	n (%)	XX	n (%)	XX	n (%)	XX
Preferred Term 1	n (%)	XX	n (%)	XX	n (%)	XX	n (%)	XX	n (%)	XX
Preferred Term 2	n (%)	XX	n (%)	XX	n (%)	XX	n (%)	XX	n (%)	XX
System Organ Class 2	n (%)	XX	n (%)	xx	n (%)	XX	n (%)	XX	n (%)	XX
Preferred Term 1	n (%)	XX	n (%)	XX	n (%)	XX	n (%)	XX	n (%)	XX
Preferred Term 2	n (%)	XX	n (%)	XX	n (%)	XX	n (%)	XX	n (%)	XX

Table 14.3.1.1TEAEs by System Organ Class and Preferred TermSafety Population

^[1] Total includes both Cohorts 1 and 2.

...

Note: At each level of summation (overall, system organ class, preferred term), subjects reporting more than one adverse event are counted only once. path/t_program.sas date time

Table 14.3.1.2 TEAEs by System Organ Class, Preferred Term and Maximum Severity Safety Population

				Coh	nort 1			
System Organ Class /		0.5	x 10 ⁶ hRPC (N=)					
Preferred Term	Mild	Moderate	Severe	Life Threatening	Mild	Moderate	Severe	Life Threatening
Subjects Reporting at Least One TEAE	n (%)	n (%)	n (%)	n (%)	n (%)	n (%)	n (%)	n (%)
System Organ Class 1	n (%)	n (%)	n (%)	n (%)	n (%)	n (%)	n (%)	n (%)
Preferred Term 1	n (%)	n (%)	n (%)	n (%)	n (%)	n (%)	n (%)	n (%)
Preferred Term 2	n (%)	n (%)	n (%)	n (%)	n (%)	n (%)	n (%)	n (%)

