ind c		Month 6	Date9. (xx)	Goldmann VF	XXXXXXXX	Normal						Normal					
		Month 12 Early Terminatio	orDate9. (xx)	Humphrey 10-2	XXXXXXXX	Normal						Abnormal Cs	Not Applicable				

Note: CS=Clinically Significant, NCS=Not Clinically Significant. path\l_program.sas date time

Programmer Note: If NO marked for testing, include reason in "Assessment Date" column. Programmer Note: Include Description of Abnormality and Clinically Significant information in "Result" column

Listing 16.2.7.1 Adverse Events

			Verbatim Term //	· (Onset Time						
			System Organ						Relationship		
Treatment	Subject		Class//Preferred	Onset Date		End Date			to Study	Treatment	
Group	ID	AE#	Term	(Study Day)		(Study Day)	Serious	Severity	Drug	of Event	Outcome
Cohort 1 - 0.5 x	XXXXXX			Date9.(xx)	Time5.	Date9.(xx)	Yes	Mild	Not Related	None	Recovery/Resolved
				Date9.(xx)	Time5.	Date9.(xx)	No	Moderate	Unlikely Related	Medication	Recovery/Resolved W/Seq
				Date9.(xx)	Time5.	Date9.(xx)	No	Moderate	Possibly Related	Non-Drug Treatment	Recovering/Resolving
				Date9.(xx)		Date9.(xx)	No	Mild	Related	Hospitalization	
				Date9.(xx)		Date9.(xx)	No	Severe	Unlikely		
									Related		
				Date9.(xx)		Date9.(xx)	No	Mild			

.....

.

Cohort 2 - 0.5 x xxx--xxx 10^6 hRPC

path\l_program.sas date time

Programmer Note: sort by subject and AE # subject

.

.....

Listing 16.2.7.2 Serious Adverse Events

Treatment Group	Subject ID	AE #	Verbatim Term // System Organ Class//Preferred Term	Onset Date (Study Day)	Onset Time	End Date (Study Day)	Severity	Relationship to Study Drug	Treatment of Event	Outcome
Cohort 1 - 0.5 x 10 ⁶ hRPC	xxxxxx			Date9.(xx)	Time5.	Date9.(xx)	Mild	Not Related	None	Recovery/Resolve d
				Date9.(xx)		Date9.(xx)	Moderate	Unlikely Related	Medication	Recovery/Resolve d W/Seq
				Date9.(xx)		Date9.(xx)	Moderate	Possibly Related	Non-Drug Treatment	Recovering/Resol ving
				Date9.(xx)		Date9.(xx)	Mild	Related	Hospitalization	e
				Date9.(xx)		Date9.(xx)	Severe	Unlikely Related	•	
				Date9.(xx)		Date9.(xx)	Mild			

Cohort 2 - 0.5 x xxx--xxx 10^6 hRPC

path\l_program.sas date time

Programmer Note: sort by subject and AE # subject

Listing 16.2.7.3 Related Adverse Events

Treatment Group	Subject ID	AE #	Verbatim Term // Preferred Term	Onset Date/Time (Study Day)	End Date (Study Day)	Serious	Severity	Relationship to Study Drug	Treatment of Event	Outcome
Cohort 1 - 0.5 x 10 ⁶ hRPC	xxxxxx			Date9.(xx)	Date9.(xx)	Yes	Mild	Related	None	Recovery/Resolved

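### AE tables and listings carry no laterality, so study-eye and fellow-eye TEAEs are pooled by cohort and dose and the injected eye's AE profile cannot be read from them

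*SAP*

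**What the plan says.** Protocol section 3.1 has one eye injected per subject, and Protocol section 2.1 and SAP section 2.1 make safety and tolerability the primary objective. One criterion in Protocol section 3.2.2 is "No clinically significant adverse events attributable to investigational product (jCell) injection".

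For adverse events, the SAP gives these rules:

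- Section 10: "Summaries of AEs will be generated by type (AE or SAE), body system and preferred term, severity, and relationship to study product".
- Section 10.2: "Each adverse event summary will be displayed by treatment group". The first summary listed there is "Subject and event incidence of TEAEs by MedDRA system organ class and preferred term". The others add highest severity, relatedness or seriousness.
- Appendix C, Table 14.3.1.1: "At each level of summation (overall, system organ class, preferred term), subjects reporting more than one adverse event are counted only once". Table 14.3.1.2 counts the subject at maximum severity, and Table 14.3.1.3 at the closest relationship.

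On data collection, Protocol section 9.1 states: "The information to be collected includes the nature, date and time of onset, intensity (mild, moderate, severe, life-threatening, death), duration, causality". Outcome follows in the same list; the affected eye is not named. The shells for Listings 16.2.7.1 to 16.2.7.3 have no eye column, whereas the shell for Listing 16.2.4.3 (ocular medical history) has one.

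SAP section 10.7 and the table list treat examination findings differently. Slit lamp, fundus photography, IOP, B-scan, dilated fundoscopy, OCT, fluorescein angiography and autofluorescence are each shown for the study eye and the non-study eye.

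**The concern.** In a single-arm trial with one injected eye per subject, the fellow eye is the only concurrent comparator, and the affected eye is the most informative attribute of an ocular event. SAP section 10.3 itself expects the product to stay in the eye. Background ocular events can occur in either eye: Protocol section 1.1.1 says that people with RP often develop early cataract or retinal edema.

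The AE tables do not use this information. A fellow-eye event and an injected-eye event under one preferred term fall in the same row of the same dose column. The counting rules then merge them within a subject: a mild injected-eye event and a severe fellow-eye event under one term appear as one subject with a severe event. At subject level, a bilateral event looks the same as a unilateral one.

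At stake is whether a reader of the AE tables can say how often, how severely and how seriously the injected eye was affected at each dose, and how that compares with the fellow eye.

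**Working it through.** The plan states no figure on this point, so there is none to reproduce. The check has two parts.

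**1. Is the eye a dimension anywhere in AE reporting?**

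| Place | Dimensions shown | Eye? |
|---|---|---|
| SAP 10 and 10.2 | group, AE or SAE, SOC, preferred term, severity, relationship | No |
| Tables 14.3.1.1 to 14.3.1.4 | cohort and dose, SOC, preferred term, plus severity, relatedness or seriousness | No |
| Listings 16.2.7.1 to 16.2.7.3 | term, onset, end, severity, relationship, treatment, outcome; seriousness in 16.2.7.1 and 16.2.7.3 | No |
| Protocol 9.1 data items | nature, onset, intensity, duration, causality, outcome | Not named |
| Listing 16.2.4.3 (ocular history) | condition, dates, eye | Yes |
| SAP 10.7 examination tables | finding by visit and eye | Yes |

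**2. How far can pooling move a reported percentage?**

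Inputs from the documents: each cohort has dose cells of 4, 4, 3 and 3, so planned N = 2 × (4 + 4 + 3 + 3) = 28, matching the synopsis. A subject counts once per term.

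- *One subject whose only event under a term is in the fellow eye.* The cell percentage rises by 100/n: 100/4 = 25.0 points, or 100/3 = 33.3 points. In the Total column it rises by 100/28 = 3.6 points. This needs no assumption about risk.

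The remaining figures are illustrations. The documents give no per-eye AE risk, so the risks below are assumed.

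- *Chance that a cell contains at least one fellow-eye event*, 1 − (1 − p)^n, for p from 5% to 20%: 14% to 49% with n = 3, 19% to 59% with n = 4, and 76% to 99.8% across 28 subjects.
- *Pooled subject incidence with independent eyes*, 1 − (1 − p_study)(1 − p_fellow):

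| Study eye | Fellow eye | Pooled | Pooled ÷ study eye |
|---|---|---|---|
| 5% | 5% | 9.75% | 1.95 |
| 10% | 10% | 19.0% | 1.90 |
| 20% | 20% | 36.0% | 1.80 |
| 30% | 30% | 51.0% | 1.70 |
| 30% | 10% | 37.0% | 1.23 |

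At 10% in each eye, this is 28 × 0.19 = 5.3 expected subjects, against 28 × 0.10 = 2.8 for the study eye alone.

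Independence is the unfavorable end of the range. If every affected subject had the event in both eyes, pooled and study-eye subject incidence would be equal (ratio 1.0). For equal risks of 5% to 30%, the ratio therefore runs from 1.0 under complete concordance to 1.70–1.95 under independence.

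**The case against.** **Eye-level safety data are already tabulated.** Section 10.7 shows cataract type and grade and IOP, among other findings, for each eye. A reader might infer that the plan throws away the within-subject control. It does not; the control is missing only from AE reporting. This narrows the point but does not remove it. Protocol section 8.1.5 presents the examinations as a way to find eye AEs that ordinary reporting may miss, which makes them a supplement. AE severity, causality and seriousness are summarized only in the unsplit AE tables. Procedure-related pain, a criterion in Protocol section 3.2.2, has no by-eye examination table.

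**No rule credits a fellow-eye event to the injected eye.** A reader might infer that such events are counted as the treated eye's. The tables count subjects and events within a dose column and attribute neither to an eye. The objection is right.

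**SOC rows separate ocular from systemic events.** Largely, yes. The ocular history shell does spread ocular terms over congenital, eye, nervous system and surgical classes. That is limited evidence for AE tables, because Protocol section 9.1 excludes procedures from AEs. In any case, SOC never separates one eye from the other.

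**The related-event table filters on causality.** A fellow-eye event judged unrelated drops out of Table 14.3.1.3. This depends on open-label investigator judgment, and section 10.2 counts missing relationship as related. Tables 14.3.1.1, 14.3.1.2 and 14.3.1.4 have no such filter.

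**The eye may be recorded.** The verbatim term is listed and may name the eye, and the CRF is not among the documents. This stands as a reason not to claim that the data are absent. Neither document requires the eye to be recorded, and no planned table uses it.

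**Conclusion.** The point holds as one of presentation. The AE tables and listings have no eye dimension, so study-eye and fellow-eye TEAEs are pooled by cohort and dose, and the injected eye's AE incidence, severity, relatedness and seriousness cannot be read from summaries that serve the primary safety objective. The firm size is 25.0 or 33.3 points in a dose cell for one subject with a fellow-eye-only event, given the planned cells of 4 and 3.

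A reader might go further and infer that pooling doubles the apparent event rate. The documents do not support that. They give no per-eye risk, near-doubling needs similar risks in eyes that behave independently, and the subject-level excess vanishes if events are bilateral. Nor do they name a single primary safety analysis that would be biased; they state a primary safety objective, to which the AE tables contribute together with the by-eye examination tables.

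The conclusion assumes that the AE shells are programmed as drawn. If the CRF records the eye, or verbatim terms name it, the remedy needs only derivation and display.

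**What to change.** - Derive an eye variable for each AE (study eye, non-study eye, both, non-ocular) from the CRF if it is recorded there, otherwise from the verbatim term. Flag events whose laterality cannot be determined as unknown; do not impute them to an eye.
- Add this variable to Listings 16.2.7.1 to 16.2.7.3.
- Present each of Tables 14.3.1.1 to 14.3.1.4 separately for study-eye ocular, non-study-eye ocular and non-ocular TEAEs, and count bilateral events in both eye panels. Apply the once-per-subject, maximum-severity and closest-relationship rules within each panel. The denominator stays the number of subjects in the column, since each subject contributes one study eye and one fellow eye. Show any events of unknown laterality as a separate line.
- State the derivation in SAP section 10.2 before database lock.

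The cost is one coding step and additional table panels for at most 28 subjects. SAP Appendix A already allows extra listing variables and the splitting of tables during programming. The remaining limitation is that some events may stay of unknown laterality.
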